### 1.0 Background

Sedentary behavior (SB) is a strong modifiable risk factor for developing type 2 diabetes (T2D) and cardiovascular disease, even after controlling for daily physical activity. During sedentary behavior, there is no muscle contraction of the legs, which causes decreasing insulin sensitivity, glucose uptake, vascular dysfunction, and promotes low-grade inflammatory cascades. Despite the important role of sedentary behavior in managing T2D, people with T2D remain highly sedentary. They spend on average 11-15 hours per day sitting, which comprises 65-75% of waking time. Moderate-to-vigorous levels of physical activity or exercise can attenuate cardiometabolic risk but does not eliminate the increased risk associated with high sedentary time. Considering T2D patients' low cardiorespiratory fitness and low activity levels, they may be at greater risk than others for the negative cardiometabolic consequences of sedentary behavior. Therefore, there is a pressing need to develop novel strategies to reduce SB and improve daily activity in patients with T2D. Targeting SB, which occupies most of a T2D patient's waking time, can be a new target behavior for secondary prevention in this population.

# 2.0 Rationale and Specific Aims

Frequent standing/walking can reduce the total SB time and change prolonged patterns to interrupted patterns. Since leg muscles do not contract during SB, sedentary breaks such as standing/walking (requiring muscle contractions) may change physiological pathways and improve cardiometabolic outcomes. A recent meta-analysis found that while controlling for total sedentary time and MVPA time, short sedentary breaks (2-5 minutes of standing/walking for every 20-60 minutes of sitting) were beneficially associated with cardiometabolic markers; adding one break decreases 0.05 unit of BMI, 0.2 cm of WC, 0.002 mg/dl of hsCRP, and 1.8 mmHG of systolic blood pressure (BP). Many intervention studies have also shown that breaking prolonged sedentary time with short periods of light PA or standing improves glucose (2-17%) and insulin (15%).  Moreover, emerging evidence shows that reducing SB time with frequent breaks is safe in other chronic health conditions and applicable to T2D patients.

SB breaks can be achieved through self-monitoring and prompts from a wearable device. In addition, the use of a smart water bottle may be a promising strategy to naturally break sedentary time due to the impact of increased water intake on kitchen and restroom breaks. A smart water bottle can sync with an activity tracker, which could synergistically motivate the T2D patients to reduce SB. This new technique is a potentially low-cost and sustainable strategy to deliver SB reduction interventions.

Because there is no SB reduction program specifically focusing on sedentary breaks in T2D patients, we propose to develop and conduct a pilot study RCT to test a wearable

technology-based SB reduction intervention in T2D patients. The 8-week intervention includes: 1) one instructional and goal setting session; 2) the use of a wearable device (Fitbit) that provides stand/walk prompts and self-monitoring; 3) a smart water bottle (HidrateSpark) that syncs with the Fitbit; 4) weekly tailored text messages for behavior reinforcement and weekly goal monitoring, and 5) one mid-program counseling session. Since text messages and wearable device-based intervention requires a complex and multiple iterative process to customize research participants' needs and refine the contents and frequency of the text messages.

Outcomes will be measured at baseline and post-intervention. Specifically, we aim to: Aim 1: Determine the acceptability of the SB reduction intervention in T2D patients by evaluating satisfaction and compliance with the intervention.

Aim 2: Evaluate the preliminary efficacy of the SB reduction intervention on changes in total SB time and numbers of prolonged SB bouts.

Aim 3 (Exploratory Aim): Explore preliminary effects of the SB reduction intervention on light physical activity (total standing and stepping times), cardiometabolic markers (24-hour glycemic control, BMI, waist circumference, blood pressure, and patient-centered outcomes (confidence in reducing SB, habit strength for SB, and quality of life).

# 3.0 Inclusion/Exclusion Criteria

Inclusion criteria: 1) ages 18 and above, 2) diagnosed with type 2 diabetes, 3) self-reported HbA1C<13, 4) self-report of sitting  $\geq$  8hr/day, 5) ability to stand and walk, 6) ownership of a smartphone.

Exclusion criteria: 1) currently using an activity tracker; 2) currently participating in exercise or other research programs; 3) random blood glucose >300; 4) non-English speaking; 5) patients who are classified as unstable (e.g., heart failure, uncontrolled arrhythmia) or have kidney disease that limits daily water intake; 6) any conditions that prevent standing or walking due to physical or cognitive limitations, such as cognitive impairment, severe pain, problems with lower limbs, or a history of surgeries that limit movement ; 7) participation in Sit Less Program V1 (IRB #221566); and 8) currently pregnant.

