### 2) Reporting Workbench

Reporting Workbench Reports are available/viewable in eStar. These reports are developed using real-time data and can be customized to meet study-specific inclusion/exclusion criteria that are computable in the EHR. The reports often include additional variables to facilitate study team outreach, such as Research OK to Contact status, MHAV account status, contact information, next upcoming appointment in a specific clinic. While the report displays certain variables/data, it provides easy access to a patient's record for additional screening and confirmation of eligibility. Research team members with appropriate eStar access can view/run the reports as frequently as needed.

We plan to use the results from our custom Reporting Workbench report to facilitate outreach in the following way: To send My Health at Vanderbilt (MHAV) recruitment requests, as detailed below in recruiting strategy 3. KSP do not have an existing provider relationship with the patients being approached about study participation. Results will be restricted to those marked as 'OK to Contact'. We will not be reaching out to employees or persons of interest.

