### **5.0 Study Procedures**

### 5.1 Baseline visit 1: Initial contact, screening, and consent

Interested respondents will be screened by a trained research staff over the phone or inperson, depending on the recruitment methods. For this research, no aspect of the participant's diabetes treatment regimen will be modified.

Those who are eligible for the study will be invited to the in-person visit. The first visit (i.e., Baseline visit 1) will be conducted at VUSN (Vanderbilt School of Nursing)'s lab at Wesley building.

At the Baseline visit 1, individuals will check their blood glucose level via finger prick. If their random glucose levels are between 80-300, they will complete the informed consent with assistance from the trained research staff. The trained research staff will complete baseline biometric assessment, including measure of height, weight, waist circumference, and blood pressure. Those who are consented will participate in: 1) completing survey questionnaires (30 minutes), 2) a baseline biometric assessment, 3) brief instruction regarding the wear of activPAL and continuous glucose monitoring (CGM) devices (30minutes), and 4) start to wear two devices for 7 days. The activPAL3 device (PAL Technologies Ltd., Scotland, UK) will be worn on the thigh and a CGM (Abbott FreeStyle Libre) will be attached to the upper arm. The research staff will provide: 1) a copy of the informed consent form; 2) instructions with photos and 5 waterproof dressings (Tegaderm) for attaching the activPAL on the thigh; 3) information about the CGM; and 4) daily sleep diary and wear log for 7 days. Participants will receive \$25 for baseline visit 1.

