### 2. Questionnaires

Participants will be given an iPad to answer questions about their demographics, socioeconomic characteristics, and a series of questionnaires detailed below. All responses will be recorded in REDCap.

- A) **Demographics**: demographics and socio-economic status will be self-reported by the patients.
- B) Health behavior: Questions about their tobacco use, alcohol intake, physical activity will be measured using the 27-item International Physical Activity Questionnaire (IPAQ), and diet measured using the 16-item Rapid Eating and Activity Assessment for Participants Short Version (REAP-S). Sleep quality (measured using the 10- item Pittsburgh sleep quality index) will be answered with the assistance of the study team member.
- C) Confidence in reducing SB and increasing PA: Confidence in reducing SB and increasing physical activity will be measured using 12 items from the Self-Efficacy Questionnaire for Physical Activity and Sedentary Behavior (Cronbach's alpha = 0.79).
- D) Habit strength for SB: Habit strength for SB will be assessed by using a validated measure, Self-Report Habit Index (Cronbach's alpha = 0.91). This 7- item index was adapted to sedentary breaks (standing/walking) to assess the degree to which sedentary breaks become habitual.
- E) **Quality of life**: Quality of life will be measured using the Patient-Reported Outcomes Measurement Information System (PROMIS)-Global Health, a 10item measure developed by the NIH as an indicator for Healthy People.
- F) **Medical history and current medication**: Medical history and current medication will be self-reported by the patients through the Self-Administered Comorbidity Questionnaire (SCQ).
- G) **Diabetes self-management**: Self-efficacy of diabetes self-management will be measured by the Diabetes Self-Management Questionnaire (DSMQ).
- H) **Diabetes-related emotional distress:** The emotional impact of living with diabetes will be assessed using the Diabetes Distress Scale (DDS).

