### 5.3.3 Smart Water Bottle

We will provide a HidrateSpark water bottle, and the study team member will assist participants in downloading the app and creating an account. The study team member will instruct participants on how to use the bottle, with the official user manual. The device alerts participants with a color change and message on the Fitbit to keep them hydrated. The device provides the daily water intake summary in the Fitbit app. We will advise participants to drink 4.5 – 6 bottles (500ml/bottle) of water per day based on current recommendations by the U.S. National Academies of Medicine. The HidrateSpark accounts require a unique email address for each user and the same email which is used to Fitbit account will be used to the HidrateSpark app. The same rules will be applied to the HidrateSpark account, and the account information will be stored in protected PI's computer within encrypted documents. Once the intervention is concluded, HidrateSpark data will not be collected. Also, the HidrateSpark bottle and the app will be reset for the participant to keep using the bottle.

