### 8.0 Statistical Considerations

Based on Sit Less V1's (IRB #221566) effect size of 0.71 for reducing sitting time, we estimated a minimum sample size of 66. To assess the scalability of Sit Less V2, we aim to recruit 80 patients. Eligible participants will include T2D patients from VUMC who report sitting for over 10 hours daily, own a smartphone, and do not currently use an activity tracker. We will screen potential participants using VUMC's electronic health records (EHR) and send recruitment messages via the My Health at Vanderbilt app. According to our EHR search, we have 2,125 eligible patients, and with a 4% recruitment rate — as seen with enrolling 7 participants monthly from Sit Less V1 — reaching a target of 80 participants within 12 months is achievable.

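### Exclusion 5 covers a daily water limit only when kidney disease is the cause, while section 5.3.3 advises 2.25 to 3.0 litres a day without exception (minor safety wording point)

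*Combined protocol and SAP*

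**What the plan says.** Exclusion 5 in section 3.0 (Inclusion/Exclusion Criteria) lists "patients who are classified as unstable (e.g., heart failure, uncontrolled arrhythmia) or have kidney disease that limits daily water intake". No other inclusion or exclusion item mentions water or fluids.

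Section 5.3.3 (Smart Water Bottle) states: "We will advise participants to drink 4.5 – 6 bottles (500ml/bottle) of water per day". It attributes the amount to a national recommendation. The same section adds a prompt: "The device alerts participants with a color change and message on the Fitbit to keep them hydrated".

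Higher intake is part of the mechanism. Section 2.0 expects the bottle to break up sitting time "due to the impact of increased water intake on kitchen and restroom breaks".

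Several general checks are described:

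- Section 4.0, under Reporting Workbench, gives staff access to the patient's "record for additional screening and confirmation of eligibility".
- Section 8.0 says potential participants are screened using the institution's "electronic health records (EHR) and send recruitment messages via the My Health at Vanderbilt app".
- Section 5.1 says: "Interested respondents will be screened by a trained research staff over the phone or inperson, depending on the recruitment methods".
- The questionnaire list in section 5.1 says: "Medical history and current medication will be self-reported by the patients".
- Section 7.0 lets the investigator discontinue a participant who would be harmed by staying in.

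**The concern.** By excluding people whose kidney disease restricts water, the plan accepts that a fluid limit and this intervention do not go together. The rule is tied to one cause of the limit rather than to the limit itself. Someone with the same instruction from a clinician for a different reason passes the criterion as written.

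What is at stake is individual safety. Such a participant, if randomized to the intervention, would be advised by the study and prompted by a device to drink an amount that may exceed what their own clinician allows. Nothing in the estimates for Aims 1 to 3 depends on this.

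**Working it through.** **Step 1. The advised volume.** Inputs from section 5.3.3: 4.5 to 6 bottles a day, 500 ml each. The plan gives bottles only, so there is no litre figure of its own to reproduce.

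- Lower end: 4.5 × 0.5 L = 2.25 L/day
- Upper end: 6 × 0.5 L = 3.0 L/day
- Duration: 8 weeks × 7 = 56 days

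**Step 2. Exclusion 5 read as a rule.** A person is excluded if classed as unstable, or if they have kidney disease that restricts water intake. Applied to the possible cases:

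| Case | Excluded by criterion 5? | Conflict with the advice possible? |
|---|---|---|
| Fluid limit because of kidney disease | Yes | No, not enrolled |
| Fluid limit for another reason, classed as unstable | Yes | No, not enrolled |
| Fluid limit for another reason, not classed as unstable | **No** | **Yes, if allocated to the intervention** |
| No fluid limit | Not on this ground | No |

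The third row is the gap. The documents name no particular condition in that row, and none is assumed here.

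**Step 3. Does the advice carry its own exception?** Section 5.3.3 gives no individual adjustment and no instruction to defer to the participant's clinician. The tailoring in section 5.3.4 concerns message frequency, activity choices and progress toward goals. It does not mention fluid volume.

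**Step 4. Would another step catch the case?**

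| Step | Where | Tied to a fluid limit? |
|---|---|---|
| Record access and EHR screening | Section 4.0 (Reporting Workbench), section 8.0 | No. Described for the EHR and patient-portal route; no record check is stated for the email list |
| Screening by trained staff | Section 5.1 | Only as far as the written criteria go |
| Self-reported history and medication at baseline visit 1, before randomization at visit 2 | Sections 5.1 and 5.2.2 | No, and not described as an eligibility re-check |
| Study phone for questions | Section 9.0 | No. Depends on the participant asking |
| Investigator discretion to discontinue | Section 7.0 | No. Acts after enrolment |

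Any of these might pick up a case, but none is written to do so.

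**Step 5. Ceiling on exposure.** With 1:1 allocation (section 5.2.2), the intervention arm has 66 / 2 = 33 people at the minimum sample size or 80 / 2 = 40 at the recruitment target (section 8.0). That is everyone who receives the advice. It is not an estimate of the number with an uncovered fluid limit, for which the documents give no basis.

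**The case against.** The best case for leaving the text alone has four parts.

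**The team already saw the hazard, and people stand between it and the participant.** Staff screen all interested respondents, medical history is taken before randomization, and a team member explains the bottle in person. This stands as mitigation and is a reason to expect few cases. It does not change the criterion that the screeners are asked to apply.

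**The decisive documents are not available.** The pre-screening survey, screening script and consent form could contain a fluid question or a caution to check with a doctor. This also stands, and nothing is inferred from their absence. Even if they do ask, the written criterion should match what is asked.

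**The intake is advice, not a required dose.** No minimum is enforced, water intake is not a listed outcome, and a participant may follow their own clinician. That lowers the likelihood of harm. It does not justify giving conflicting advice. The statement in section 6.0 that the bottle carries no risk is about using the bottle. Treating it as a claim about fluid volume would be an interpretation, and this point does not rely on it.

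**Heart failure is already excluded.** A reader might infer a second gap, that stable heart failure is let in because heart failure appears only as an example of instability. The text does not support that as a separate finding. The arrhythmia example is qualified as uncontrolled while heart failure is left unqualified, so the more natural reading is that heart failure itself excludes. At most the wording is ambiguous, and the fix below makes the ambiguity harmless for anyone with a fluid limit.

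**Conclusion.** The point holds as a minor, low-priority wording matter. Exclusion 5 is narrower than the hazard it addresses: a medically advised fluid limit from a cause other than kidney disease, in someone not classed as unstable, is not covered, and the advice of 2.25 to 3.0 L/day has no exception.

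The number affected is unknown and probably small. A reader might be tempted to apply an assumed percentage to the 33 or 40 intervention participants to get a headcount. The documents give no such percentage, so the result would only restate the assumption.

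The conclusion assumes that exclusion 5 is applied as written and that no unseen screening document already asks about fluid limits in general. It does not depend on how heart failure is read. It implies no change to the aims, sample size or analysis, and it does not say the advised volume is wrong for participants without a fluid limit. That is for the study's clinicians to judge.

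**What to change.** Replace the kidney-disease clause at the end of exclusion 5 with: *or have been medically advised to limit daily fluid intake, for any reason*. This keeps the kidney-disease case and also covers anyone with heart failure who has a fluid limit.

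Apply the reworded criterion in the eligibility screen of section 5.1 for all recruitment routes, including the email distribution list.

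The cost is one clause in a minor amendment and, if the screen does not already ask, one question. The only downside is possibly a few fewer eligible people.

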### 4.0 Enrollment/Recruitment

We will use three recruitment strategies:

# 1) Research Notification Distribution List

Email distribution list allows researchers to email IRB-approved participant recruitment announcements to the Vanderbilt community. Members of the distribution list have the option to subscribe/unsubscribe with each email. The

potential participants will click the pre-screening consent. The detailed procedure regarding pre-screening prospective participants is described below

### 2) Reporting Workbench

Reporting Workbench Reports are available/viewable in eStar. These reports are developed using real-time data and can be customized to meet study-specific inclusion/exclusion criteria that are computable in the EHR. The reports often include additional variables to facilitate study team outreach, such as Research OK to Contact status, MHAV account status, contact information, next upcoming appointment in a specific clinic. While the report displays certain variables/data, it provides easy access to a patient's record for additional screening and confirmation of eligibility. Research team members with appropriate eStar access can view/run the reports as frequently as needed.

We plan to use the results from our custom Reporting Workbench report to facilitate outreach in the following way: To send My Health at Vanderbilt (MHAV) recruitment requests, as detailed below in recruiting strategy 3. KSP do not have an existing provider relationship with the patients being approached about study participation. Results will be restricted to those marked as 'OK to Contact'. We will not be reaching out to employees or persons of interest.

### 3) My Health at Vanderbilt (MHAV) Recruitment Requests

Participants will be recruited through My Health at Vanderbilt. My Health at Vanderbilt (MHAV) is VUMC's patient portal where the patient may sign up and participate in managing his/her health care. MHAV can also be used for sending recruitment requests to a predefined cohort of patients who meet certain study-specific inclusion/exclusion criteria, have an activated MHAV account and are marked as OK to Contact in eStar. The recruitment requests are sent by a central VICTR team on behalf of the study team. The notification preferences for the recruitment requests can be managed by the patients in MHAV. The system default is an email notification like clinical notifications (see attached MHAV Recruitment Request messaging). If the patient has turned off notifications, the study will just be listed on their research studies page in MHAV.

Once the Recruitment Requests are sent, the patient's enrollment status is automatically updated to (IT Use Only) Identified - RWB Recruitment Message or

Auto DL. If the patient clicks '**No Thank You'**, the patient's enrollment status in eStar is automatically updated to **(IT Use Only) Not Interested - Pt. answered in MHAV**. The study team does not get a notification in Epic In-Basket or in REDCap.

If the patient clicks '**I'm Interested**', the designated KSP (with eStar access) receive an In Basket message in eStar indicating the patient is interested

The patient's enrollment status is automatically updated to **(IT Use Only) Interested - Pt. answered in MHAV**. The REDCap Participant Updater Module looks for the patient's MRN in the study specific database. If a matching MRN is not found, the Participant Updater Module creates a record in the study-specific database with the following information from eStar:

- 1) Patient's MRN
- 2) Patient's enrollment status (IT Use Only) Interested Pt. answered in MHAV
- 3) Study ID (IRB#)

REDCap CDIS is then triggered to pull in the patient email address from eStar if available for all patients who click I'm Interested. This will trigger an email from REDCap to the patient which contains a link to the IRB approved pre-screening and eConsent surveys on REDCap.

If the patient responds to the email from REDCap or completes a pre-screening survey or eConsent, the study team will update the patient's enrollment status accordingly in eStar or REDCap. Once the patient's enrollment status has been updated in the study specific record in REDCap, the Participant Updater Module will automatically update the enrollment status in eStar. The study team will contact the interested patient by telephone call or email to confirm their eligibility and schedule an in-person baseline visit

